#### **14.3.3 Subgroup analyses**

Subgroup analyses will be performed on the ACR50 response and the PASI90 response at Week 16. The following variables for subgroup analyses will be defined:

- Age (<45 years of age,  $\geq$ 45 years of age)
- Gender (male, female)
- Disease duration (<1 year,  $\geq$ 1 year)
- Region (eg, Asia, Eastern Europe, North America, Western Europe)
- Race
- Weight at Baseline ( $\leq$ 100kg,  $>$ 100kg)
- Bone erosion ( $\geq$ 1) at Baseline (Yes, No)
- hs-CRP at Baseline ( $<$ 6mg/L,  $\geq$ 6mg/L)
- Bone erosion ( $\geq$ 1) and/or hs-CRP  $\geq$ 6mg/L at Baseline (Yes, No)
- Prior cDMARDs (0, 1,  $\geq$ 2)
- Concomitantly receiving cDMARDs versus no concomitant cDMARDs
- Concomitantly receiving MTX versus no concomitant MTX
- PSO affected BSA at Baseline ( $<$ 3%,  $\geq$ 3% to 10%,  $>$ 10%)
- BASDAI at Baseline ( $\leq$ 4,  $>$ 4)

---

- Anti-bimekizumab antibody status (positive, negative)
- HLA-B27 (positive, negative)

## **14.4 Planned safety analyses**

### **14.4.1 Safety analyses**

Safety variables will be analyzed for all subjects in the SS.

Adverse events will be coded according to the Medical Dictionary for Regulatory Activities (MedDRA® 19.0). Adverse events with an onset date on or after the date of first IMP administration and up to 20 weeks after the last (most recent) dose of IMP will be defined as TEAEs. Treatment-emergent AEs will be summarized descriptively by treatment group, primary system organ class, high-level term, and preferred term. Additional tables will summarize TEAEs leading to withdrawal from IMP, TEAEs by intensity and relationship to IMP.

Treatment-emergent AEs leading to withdrawal from both IMP or the study, serious TEAEs, TEAEs of special interest, TEAEs of special monitoring and deaths will be also be tabulated and listed. TEAEs adjusted for exposure will also be presented.

When analyzing categorical data, the number and percentage of subjects in each category will be presented by treatment group. In addition, shift tables may be used to evaluate the number and percentage of subjects having a different post-Baseline status when compared to their baseline status.

Laboratory value (including markedly abnormal values), urinary values, vital signs, ECGs, eC-SSRS, and extent of exposure will be presented descriptively by treatment group. Definitions for markedly abnormal laboratory values will be provided in the SAP.

## **14.5 Other planned analyses**

### **14.5.1 Pharmacokinetics analyses**

Pharmacokinetic variables will be analyzed for all subjects in the PK-PPS.

Bimekizumab plasma concentrations will be summarized for each treatment at each scheduled visit.

The relationship between bimekizumab plasma concentrations and efficacy response (for example ACR20/50/70) and/or safety endpoints may be explored via a graphical and/or a model based (PK-PD) approach. The data may also be combined with that from other bimekizumab trials. The details of such analysis will be described separately in a data analysis plan, and the analysis itself will be reported separately from the CSR.

### **14.5.2 Immunological analyses**

Anti-bimekizumab antibodies will be assessed using a tiered approach: screening, confirmatory, and titer assays will be used. Anti-bimekizumab antibodies (including positivity) will be summarized by treatment at each scheduled visit at which samples are collected.

## **14.6 Handling of protocol deviations**

Important protocol deviations are deviations from the protocol, which potentially could have a meaningful impact on study conduct or on the primary efficacy, key safety, or PK outcomes for

an individual subject. The criteria for identifying important protocol deviations will be defined within the appropriate protocol-specific document. Important protocol deviations will be reviewed as part of the ongoing data cleaning process and all important deviations will be identified and documented prior to unblinding to confirm exclusion from analysis sets.

## 14.7 Handling of dropouts or missing data

The primary method for assessing the efficacy variables will be the composite estimand approach to handling missing data that is similar to NRI. The sensitivity of results to the approach for handling missing data will be evaluated via supportive analyses using different missing data mechanisms.

In instances where MI is used, the missing value is replaced by a set of plausible values, where each value is a Bayesian draw from the conditional distribution of the missing data given the observed data. Intermittent missing data will be imputed using the MCMC method, followed by regression for monotone missing data. The multiple imputation procedures planned for efficacy analyses are based on an assumption of data missing at random (MAR).

Missing data will be evaluated as sensitivity analyses using different missing data mechanisms. The following sensitivity analyses for the primary efficacy variable will be conducted:

1. Multiple imputation as described above will be performed using the modified composite estimand. The definition of an intercurrent event is changed from all treatment discontinuation, to discontinuation of treatment due to AE or lack of efficacy.
2. A tipping point analysis will be performed to evaluate missingness assumptions. The tipping point analysis will be performed on the monotone missing data and only if the primary analysis is significant at  $\alpha=0.05$ . Various delta adjustments will be made to the assumed responses on the monotone missing data in each treatment group independently with various degrees of plausibility. It will include scenarios where subjects who have missing data and are randomized to bimekizumab have a lower probability of response compared to subjects who have missing data and were randomized to placebo. For binary variables, this includes the worst-case scenario where subjects who have missing data and are randomized to bimekizumab are considered nonresponders, while subjects who have missing data and were randomized to placebo are considered responders. The goal of the tipping point analysis is to systematically vary assumptions until there is no evidence of a treatment effect (if possible). The plausibility of such required delta adjustment will then be assessed. Details will be provided in the SAP.
3. The treatment policy strategy for addressing intercurrent events will be considered. This will be based on an analysis in which all available data at Week 16 regardless of the occurrence of intercurrent events will be considered. This analysis will use the same models specified for the primary and secondary analyses where subjects are analyzed according to their randomized treatment, even if they discontinued study treatment for any reason prior to Week 16 and were no longer on the randomized study treatment when the assessment was performed at Week 16. Even though efforts will be made to collect the primary outcome data for all subjects at Week 16, there may still be some subjects for whom Week 16 efficacy data cannot be obtained. In this case, missing data will be imputed using MI under the assumption of MAR. Results will be combined into a single inference using Rubin's rule. It should be noted that this measures something different from the primary analysis and could be

---

confounded by placebo subjects who withdraw and are subsequently on another active medication at the time of the Week 16 assessment. Therefore, the results of this analysis should be interpreted in the appropriate context.

4. An additional sensitivity analysis will be based on observed data only for subjects who are still on the initially randomized treatment at Week 16. Subjects with missing data or who have prematurely discontinued study treatment will be treated as missing. The same procedure described as in the main efficacy analysis will be used.

Additional details on these sensitivity analyses will be provided in the SAP.

## **14.8 Planned interim analyses and data monitoring**

### **14.8.1 Interim analyses**

Two interim analyses will be performed: one after all randomized subjects have completed the Double-Blind Treatment Period and the Week 24 assessments, and one after all subjects have completed Week 52.

The purpose of the Week 24 interim analysis is to perform a comprehensive evaluation of all available double-blind data for the 3 treatment arms and to prepare a regulatory submission for a marketing authorization application based on this analysis.

For the Week 24 interim analysis, the database will be locked and the treatment codes will be made available to UCB personnel with exception of operational staff working on the study. An interim report will be written. The Investigators and subjects will remain blind to the assigned bimekizumab dosing regimen until the final analysis is completed.

The Week 24 interim analysis will evaluate the primary and secondary efficacy variables, as well as all other efficacy, safety, and PK variables up to Week 24 according to the statistical methods specified in the SAP. No formal alterations to the further study conduct (eg, stopping rules, sample size re-estimation, or changes to eligibility criteria) are planned for this interim analysis.

To ensure blinding of Investigators and subjects, a blinding plan will be written to evaluate the potential bias of the Active Treatment-Blind period, define blinded and unblinded teams, and describe the process of interim results generation and dissemination. The plan will be finalized prior to the lock of the database at the interim analysis.

The purpose of the Week 52 interim analysis is to perform a comprehensive evaluation of all available data for the study and to supplement the regulatory submission based on the Week 24 interim analysis.

The Week 52 interim analysis will evaluate all efficacy, safety, and PK variables up to Week 52 according to the statistical methods specified in the SAP. Only data from the SFU visits for subjects who discontinued and did not enter the extension study will not be included.

Additional data cuts may be prepared following regulatory requests or for publication purposes.

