A second interim analysis of all available data will be undertaken after all randomized subjects have completed 52 weeks of treatment or have withdrawn from IMP or the study. The purpose of this analysis is to demonstrate the long-term efficacy and safety of bimekizumab. For subjects who are ineligible for the open-label extension study at Week 52, a final analysis will be undertaken after the SFU Visit.

Additional details for the interim analyses and data monitoring in this study are provided in [Section 14.8.1](#). A detailed schedule of study assessments is presented in [Table 5-1](#) and a study schematic diagram is presented in [Figure 5-1](#).

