## **5.5 Safety Follow-Up Visit**

All subjects who complete the study and do not enter the extension study will have an SFU Visit, 20 weeks after their final dose of IMP.

Any subjects who discontinue early, including those withdrawn from IMP, will be asked to attend all scheduled visits and will have an SFU Visit, 20 weeks after their final dose of IMP.

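### Read literally, the Week 52 analysis leaves out Safety Follow-Up data of discontinued subjects even when already in hand, so TEAE incidence under the protocol's 20-week definition can be somewhat understated

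*Protocol*

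**What the plan says.** - **Scope of the Week 52 analysis.** Section 5.1: "A second interim analysis of all available data will be undertaken after all randomized subjects have completed 52 weeks of treatment". Subjects who withdrew also count toward this trigger. Section 14.8.1: "The purpose of the Week 52 interim analysis is to perform a comprehensive evaluation of all available data for the study". It also serves to add to the submission made on the Week 24 results.
- **Time limit.** The analysis "will evaluate all efficacy, safety, and PK variables up to Week 52" (Section 14.8.1).
- **Exclusion.** The sentence after that limit reads: "Only data from the SFU visits for subjects who discontinued and did not enter the extension study will not be included".
- **TEAE definition.** Section 14.4.1: events starting on or after the first dose and "up to 20 weeks after the last (most recent) dose of IMP will be defined as TEAEs". TEAE incidence is a secondary safety variable (Section 4.2.2).
- **Follow-up after stopping.** Section 5.5: "Any subjects who discontinue early, including those withdrawn from IMP, will be asked to attend all scheduled visits and will have an SFU Visit". The timing is 20 weeks from the final dose. Under Section 6.3, subjects who leave the study altogether have only the ET Visit and the SFU Visit.
- **Content of the SFU Visit.** Section 8.4 lists adverse events, laboratory samples, ECG, PK and anti-bimekizumab antibodies, among others.
- **Later analysis.** Section 5.1: "a final analysis will be undertaken after the SFU Visit". That sentence names only subjects ineligible for the extension at Week 52.

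**The concern.** An analysis described as using everything available carries a standing exclusion for one group, and the exclusion depends on the type of visit rather than its date. An SFU record collected months before the cut-off is left out in the same way as one still to come.

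The excluded visit closes the 20-week window in which the protocol calls an event treatment-emergent. For a subject who left the study after an ET Visit, it is the only scheduled contact left in that window. Non-serious events that start after the ET Visit would routinely be picked up only there, so the Week 52 TEAE tables can be incomplete against the protocol's own definition. Follow-up laboratory, ECG, PK and antibody results already in the database are dropped as well.

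The wording also fits poorly with which visits are likely to be outstanding. Completers who do not enter the extension have the latest SFU visits, yet the sentence speaks of subjects who discontinued.

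**Working it through.** The protocol gives no figure to reproduce here. The check is one of timing.

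**Inputs from the protocol.** SFU at last dose + 20 weeks, with a window of -3/+7 days (Sections 5.5 and 8). Dosing visits every 2 weeks from Week 0 to Week 50 (Table 7-1), 26 in all, so 25 possible last-dose visits for an early stopper (Weeks 0 to 48). Planned size 840.

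**Step 1: does the Week 52 limit explain the exclusion?**
SFU week = last-dose week + 20.
- Last dose at Week 32: 32 + 20 = 52, or Week 53 at the late end of the window.
- Last dose at Week 30 or earlier: 30 + 20 + 1 = 51 at the latest.
- Last dose at Weeks 34 to 48: SFU at Weeks 54 to 68.
- Completer with last dose at Week 50: SFU at Week 70.

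Weeks 0 to 32 make up 17 of the 25 early last-dose visits (17/25 = 68%). For these the SFU is nominally due by the subject's own Week 52, so the limit does not account for leaving them out.

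**Step 2: how many SFU visits would be in hand at the cut-off?**
This needs enrolment length *E* and the timing of discontinuation, which the protocol does not give; both are assumed. With uniform accrual and a cut-off at the last subject's Week 52, a subject randomized *u* weeks after the first has the visit in hand if

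last-dose week + 20 ≤ 52 + (*E* − *u*).

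Averaging over *u* and over the 25 last-dose visits:

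| Stopping pattern (assumed) | E = 0 | E = 26 wk | E = 52 wk | E = 78 wk |
|---|---|---|---|---|
| Even | 68% | 89% | 94% | 96% |
| Weighted late (weights 1 to 25) | 47% | 81% | 90% | 94% |
| Weighted early (weights 25 to 1) | 89% | 97% | 99% | 99% |
| Completers not entering the extension | 0% | 31% | 65% | 77% |

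Hand check at *E* = 0, late weighting: (1 + … + 17)/(1 + … + 25) = 153/325 = 47%. Completers at *E* = 26: 1 − 18/26 = 31%.

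The cut-off in this table is a simplification. The Section 5.1 trigger also counts subjects who have withdrawn, so the cut need not wait for a late-randomized stopper's own Week 52.

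**Step 3: upper bound on size.**
If 5-10% stop early (an assumption), 42 to 84 of 840 subjects are concerned. At 20 weeks each: 42 × 20/52 = 16 and 84 × 20/52 = 32 subject-years. Against roughly 840 subject-years over the year, that is 16/840 = 2% to 32/840 = 4%. This credits every stopper with the full window, as if all had left the study at the last dose. The true loss is smaller, because those who stay are seen at scheduled visits and an ET Visit covers part of the window.

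**The case against.** **The sentence may only list what is still outstanding.** The extension is open only to subjects who complete Week 52. If the exclusion meant early stoppers alone, the condition about not entering the extension would be redundant. That suggests the author also had in mind subjects who end treatment at Week 52 without rolling over, whose visits come later. This is a plausible intention. However, even on that wider reading early stoppers are still included, the sentence has no date limit, and records already in the database are still dropped.

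**Harms after stopping are not missing as a whole.** A reader might infer that they are, or that everyone who stopped because of harm disappears from the Week 52 safety tables. The protocol does not support this:
- Only SFU-visit data are excluded. Section 14.4.1 defines a TEAE by onset date, not by the visit that records it.
- Under Section 6.3, most withdrawals for adverse events or laboratory values are from IMP only, and these subjects are asked to attend all visits to Week 52.
- Events are also recorded at ET and unscheduled visits, SAEs are reported within 24 hours (Section 12.1.2.3), and event follow-up usually runs for 20 weeks after IMP is stopped (Section 12.1.3).

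This stands. It narrows the gap mainly to non-serious events in subjects who left the study.

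**The data are deferred, not lost.** A final analysis follows the SFU, the DMC reviews safety throughout, and further data cuts are allowed on regulatory request. This largely stands. However, the final-analysis sentence in Section 5.1 does not clearly cover early discontinuers, and DMC review does not complete the Week 52 tables.

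**Cut-off handling belongs in the SAP.** Often so, but here the protocol itself states a rule, and the rule conflicts with the stated scope of the analysis.

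**Conclusion.** The point holds in a limited form. As worded, the exclusion conflicts with the described scope of the Week 52 analysis, and the Week 52 limit does not justify it for subjects whose last dose was at or before Week 32. It can understate TEAE incidence, mainly for non-serious events in subjects with only an ET Visit and an SFU Visit, and it drops other SFU safety, PK and antibody data already collected.

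The size is modest. The 16-32 subject-years are an upper bound on an assumed stopping rate, and the number who leave the study altogether cannot be worked out from the protocol. It would also be too strong to say that discontinuers' SFU visits always precede the cut-off. In the scenarios above the share in hand runs from 47% to 99%, depending on accrual and stopping times that are not given, and the withdrawal clause in the trigger and the +7-day window can shift individual visits past the cut. No confirmatory efficacy test is affected.

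**What to change.** Replace the exclusion sentence in Section 14.8.1 with a rule based on date:

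> All SFU data collected by the Week 52 cut-off are included for every subject, using the 20-week TEAE definition of Section 14.4.1. Only SFU visits still pending at the cut-off, whether for early discontinuers or for completers not entering the extension, are deferred to the final analysis, and their number is reported by treatment group.

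This reconciles Sections 5.1, 14.4.1 and 14.8.1 and makes clear that the final analysis also takes in early discontinuers. It needs no new data. The cost is one sentence, plus flagging the pending visits at the cut-off.

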### **14.8.2 Data monitoring**

A Data Monitoring Committee (DMC) will be reviewing safety data on an ongoing basis. The DMC membership includes experienced clinicians and a statistician, all of whom have expertise in clinical studies. Further details are specified in the DMC Charter.

---

Cardiovascular and Neuropsychiatric Adjudication Committees will also periodically review data from this study. Details are provided in the Cardiovascular Adjudication Committee and Neuropsychiatric Adjudication Committee charters.

Other adjudication committees may be added as necessary.

Both Data Monitoring and Adjudication Committee members may not participate in the study as principal or co-Investigators, or as study subject care physicians and must not be members of the study team at UCB or the conducting CRO. The duration of membership for the committees will be inclusive of planned analyses for PA0010.

## **14.9 Determination of sample size**

Approximately 840 subjects will be randomly assigned in a 3:2:1 ratio to the following treatment groups: bimekizumab 160mg sc Q4W (420 subjects), placebo (280 subjects), adalimumab 40mg sc Q2W (140 subjects).

The primary efficacy analysis is based on the bimekizumab dose versus placebo for ACR50 response at Week 16. It is planned that only descriptive summaries will be provided for the adalimumab reference arm. No statistical comparisons will be made between adalimumab and the other treatment groups.

All sample size and power calculations were done at a significance level of 0.05.

All sample size and power calculations were performed using the software nQuery Advisor® 7.0.

### **14.9.1 Power calculation for primary endpoint**

The sample size assumptions for bimekizumab versus placebo are based on the ACR50 response data from the Phase 2b bimekizumab study in subjects with moderate to severe PsA (PA0008). The median ACR50 responses of the top three dose groups (bimekizumab 160mg, 320mg, and 320mg [initial dose] plus 160mg) at Week 12 in the TNF-naïve population are conservatively assumed for the Week 16 endpoint. The observed median ACR50 response rate of the top three bimekizumab doses in the TNF-naïve population in study PA0008 was 43.8%.

The placebo ACR50 response at Week 16 is based on the TNF $\alpha$ -naïve population in PA0008 (6.1% at Week 12, n=33); Mease et al, 2015), FUTURE 2 study in the subgroup of TNF $\alpha$ -naïve subjects (15.9%, n=63; McInnes et al, 2015), FUTURE 3 study (11.8%, n=93; Nash and Mease, 2018), and FUTURE 5 study in a mixed TNF $\alpha$  exposure population (8.1% at Week 16, n=332; Mease et al, 2018). Therefore, the estimated ACR50 response at Week 16 in the placebo group is assumed to be 16%.

The sample size for showing statistical superiority of bimekizumab vs placebo was calculated using a 2-sided 2-sample Chi-square test with continuity correction (Fleiss et al, 1980). Assuming 420 subjects in the bimekizumab group and 280 subjects in the placebo group, the test for detecting statistical superiority of bimekizumab 160mg Q4W vs placebo based on ACR50 response at Week 16 has >99% power to detect a true treatment difference of 27.8% (odds ratio 4.09).

### **14.9.2 Power calculations for secondary endpoints**

The assumptions for power calculations of the secondary endpoints included in the hierarchy, and for which supporting data exists, are based on the interim results of the Phase 2b

---

bimekizumab study PA0008 and the FUTURE 1, FUTURE 2, FUTURE 5, and SPIRIT P1 studies. All power calculations for binary endpoints were performed using a 2-sided 2-sample Chi-square test with continuity correction (Fleiss et al, 1980). All power calculations for continuous endpoints were performed using a 2-sided 2-group Satterthwaite t-test (Moser et al, 1989).

For the PASI90 response at Week 16, the bimekizumab 160mg Q4W treatment response at Week 12 is 45% (n=20) in the TNF $\alpha$ -naïve population of PA0008 at Week 12 and 46% (n=28) at Week 12 in the mixed TNF $\alpha$  exposure population. The placebo PASI90 response at Week 16 is based on the subgroup analyses of TNF $\alpha$  therapy-naïve subjects in PA0008 (9.1% at Week 12; n=22), FUTURE 2 study (9.7% at Week 24; n=63), and SPIRIT P1 study (1.5% at Week 12; n=67). Therefore, a placebo PASI90 response rate of 10% is assumed. With those assumptions, the study has >99% power to detect a true treatment difference at an assumed 60% of subjects with BSA  $\geq$ 3% of the planned sample size.

For change from Baseline in HAQ-DI at Week 16, the between treatment differences of the change from Baseline in HAQ-DI of in the mixed TNF $\alpha$  exposure population of the PA0008 at Week 12 were used. The bimekizumab 160mg Q4W treatment group mean change from Baseline in HAQ-DI at Week 12 of -0.37, SD=0.47 (n=41) versus placebo mean change from Baseline in HAQ-DI at Week 12 of -0.13, SD=0.50 (n=42). With those assumptions, the study has >99% power to detect a true treatment difference of -0.24 at the planned sample size.

For change from Baseline in PCS of SF-36 at Week 16, the between treatment differences of the change from Baseline in PCS of SF-36 of the TNF $\alpha$ -naïve population of FUTURE 2 study (Kavanaugh et al, 2016) at Week 24 were used. The bimekizumab 160mg Q4W treatment group assumes the secukinumab 150mg treatment group mean change from Baseline in SF-36 PCS at Week 24 of 7.91, SD 7.38 (N=63) versus placebo mean change from Baseline in SF-36 PCS at Week 24 of 2.08, SD 9.51 (N=63). With those assumptions, the study has >99% power to detect a true treatment difference of 5.83 at the planned sample size.

For MDA at Week 16, the bimekizumab 160mg Q4W treatment response at Week 12 in PA0008 is 46.3% (N=41) in the mixed TNF $\alpha$  exposure population of PA0008. In the placebo group, 14.3% of subjects achieved MDA at Week 12 (n=42). With those assumptions, the study has >99% power to detect a true treatment difference of 32% (odds ratio 5.17) at the planned sample size.

For change from Baseline in vdHmTSS at Week 16, the between treatment differences of the change from Baseline in vdHmTSS at Week 16 of the SPIRIT P1 study in a TNF $\alpha$ -naïve population (Mease et al, 2017) were used. The SPIRIT P1 study ixekizumab 80mg sc Q2W treatment group least square (LS) mean change from Baseline at Week 16 0.06 and SD 0.720; and LS mean change from Baseline 0.36 and SD 0.710 for placebo are assumed. With those assumptions, the study has a 95% power to detect a true treatment difference of -0.30, assuming 45% of subjects with elevated hs-CRP and/or bone erosion, in the planned sample size.

There is uncertainty in the final percentage of subjects with elevated hs-CRP and/or bone erosion at Baseline that will be recruited to the study and the variability in the subgroup. To demonstrate the sensitivity of the sample size calculation for this study, [Table 14-1](#) shows the power function for a fixed total sample size of 840 subjects in the RS population for this secondary efficacy analysis, varying the percentage of subjects with elevated hs-CRP and/or bone erosion at

Baseline and the treatment difference and estimated standard deviation on the change from Baseline in vdHmTSS at Week 16.

